SD-OCT	Spectral Domain Optical Coherence Tomography
SOC	System Organ Class
SOP	Standard Operating Procedures
SRF	Subretinal Fluid
TEAE	Treatment-Emergent Adverse Event
wAMD	Wet Age-Related Macular Degeneration
WBC	White Blood Cell Count
WHO	World Health Organization

1. Introduction

The purpose of this statistical analysis plan (SAP) is to describe the planned analyses and reporting for protocol ALK4290-201, Version 3.0 dated 15MAY2018 and Clarification Memorandum #1 dated 12JUL2018.

This SAP is being written with due consideration of the recommendations outlined in the most recent International Conference on Harmonization (ICH) E9 Guideline entitled Guidance for Industry: Statistical Principles for Clinical Trials and the most recent ICH E3 Guideline, entitled Guidance for Industry: Structure and Content of Clinical Study Reports (CSR).

This SAP describes the data that will be analyzed and the subject characteristics, efficacy, and safety assessments that will be evaluated. This SAP provides details of the specific statistical methods that will be used. The statistical analysis methods presented in this document will supersede the statistical analysis methods described in the clinical protocol. If additional analyses are required to supplement the planned analyses described in this SAP they may be completed and will be identified in the CSR.

2. Study Objectives

The primary objective of this study is to investigate the potential therapeutic effects of a 6-week, twice daily oral dosing regimen of ALK4290 on best corrected visual acuity (BCVA) in newly diagnosed (treatment naïve) patients with Wet Age-Related Macular Degeneration (wAMD) as measured by the Early Treatment Diabetic Retinopathy Study (ETDRS) testing method. The secondary objectives are to assess the safety of the proposed dosing regimen.

3. Study Variables

3.1 Primary Variable

- Mean change from baseline in BCVA letter score as measured by the ETDRS testing method at 6-weeks

3.2 Secondary Variable

- Safety as assessed by incidence, seriousness, and severity of adverse events (AE)

3.3 Exploratory Variables

- Changes in concentrations of ALK4290 in plasma at various time points
- Changes in central subfield thickness (CST), intraretinal fluid (IRF), subretinal fluid (SRF), and pigment epithelial detachment (PED) as measured by spectral domain optical coherence tomography (SD-OCT) and fundus photography/fundus angiography (FP/FA)
- Evaluation of pharmacogenomic characteristics and biomarkers in blood and plasma samples

3.4 Statistical Hypotheses

The null and alternative hypotheses for change from baseline in BCVA letter score as measured by ETDRS testing method are as follows:

H₀: Mean change from baseline in BCVA letter score at 6 weeks = 0

H₁: Mean change from baseline in BCVA letter score at 6 weeks ≠ 0

The hypothesis testing will be at a two-sided Type I error rate (α) of 0.20. Specifics of the statistical tests are provided in Section 14.

4. Study Design and Procedures

4.1 General Study Design

This is a single arm, open-label study to evaluate the therapeutic effects and safety of a 6-week treatment regimen of ALK4290 in patients with newly diagnosed (treatment naïve) wAMD. This study enrolls newly diagnosed patients with Choroidal Neovascularization (CNV) secondary to AMD. All subjects will receive the investigational treatment ALK4290 at a daily dosage of 800 mg administered orally twice a day as 400 mg tablets for 6 weeks. At every visit, safety and tolerability assessments will occur. At specified visits, BCVA will be measured by the ETDRS testing method and morphological evaluations will be conducted utilizing SD-OCT and FP/FA.

The study eye is defined as the eye that meets all the inclusion criteria and none of the exclusion criteria. If both eyes meet the inclusion and none of the exclusion criteria, the study is selected by the investigator, per their discretion.

The overall duration of the study is approximately 10 months from study initiation (i.e., first subject enrolled) to study completion (i.e., last subject last visit) with a targeted recruitment of 30 subjects over the accrual period. The subject participation period is 10 weeks (6-week treatment plus 4-week follow-up), unless prematurely discontinued.

4.2 Schedule of Visits and Assessments

The schedule of event table:

Visit Number Day Time Window (days)	Screening	Treatment Period							Follow-Up		
	1 -7 to -2	2 1	3 8 ±1	4 15 ±1	5 22 ±1	6 29 ±1	7 36 ±1	8/EOT ⁷ 43 ±1	9/FU 50 ±1	10/FU 57 ±1	Phone/FU 71 ±1
Informed Consent ¹	X										
Informed Consent for Pharmacogenomics ²	X										
[REDACTED]	X										
Demographics	X										
Medical history	X										
Inclusion/exclusion criteria ³	X	X									
Physical examination	X	X		X		X		X ⁷		X	
Vital signs (seated)	X	X	X	X	X	X	X	X ⁷	X	X	
Laboratory tests	X	X	X	X	X	X	X	X ⁷	X	X	
Pregnancy test (as applicable) ⁹	X	X						X			
12-lead ECG	X		X			X		X ⁷			
SD-OCT	X	X	X	X	X	X	X	X ⁷	X	X	
FP/FA	X							X ⁷			
Visual acuity	X	X	X	X	X	X	X	X ⁷	X	X	
Slit-Lamp	X	X	X	X	X	X	X	X ⁷	X	X	
IOP	X	X	X	X	X	X	X	X ⁷	X	X	
Administration of study agent ⁴		X	X	X	X	X	X	X ⁷			
Dispense study agent		X	X	X	X	X	X				
Study agent accountability		X	X	X	X	X	X	X ⁷			
Pharmacokinetic (PK) blood sample (for plasma extraction)		X ⁵	X ⁶	X ⁶	X ⁶	X ⁶	X ⁶	X ^{5,7}	X		
Biomarker plasma aliquots		X ⁵				X ⁵		X ^{5,7}	X ⁵		
[REDACTED]		X ²									
Adverse events ⁸	X	X	X	X	X	X	X	X ⁷	X	X	X
Concomitant/current medications ⁸	X	X	X	X	X	X	X	X ⁷	X	X	X
Trial completion											X

1. All subjects must sign an informed consent consistent with ICH-GCP guidelines prior to any trial related procedures, which includes medication washouts and restrictions.
2. [REDACTED]
3. A preliminary check of inclusion/exclusion criteria will be performed at screening (Visit 1) after obtaining informed consents.
4. Study agent will be self-administered in the clinic under supervision of study personnel during every visit of the treatment period (Visits 2-8) following all safety and ophthalmic assessments. Training on study agent administration will be conducted prior to the initial study agent administration at Visit 2.
5. A pre-dose PK blood sample will be taken to be centrifuged for collection of plasma samples. Biomarker plasma aliquots will be obtained from the PK samples. At Visit 2 only, four post-dose PK blood samples will be taken.
6. A pre-dose PK blood sample will be taken to be centrifuged for collection of plasma samples.
7. End of Treatment (EOT) visit (Visit 8): all study related procedures will be conducted at the conclusion of 6 weeks of treatment on Day 43 ±1. Withdrawal of consent is allowed at any time. For subjects who withdraw consent from the study, no study procedures will be done thereafter. For those that withdraw from the study agent, follow-up visits are to occur as per the protocol. Excluding cases of medical emergency, but prior to the discontinuation of a subject from the clinical study for disease worsening, the study investigator should discuss each case of discontinuation with the sponsor.
8. Adverse events and concomitant medications will be assessed at every study visit as well as recorded at any unscheduled subject contact (e.g., unscheduled phone calls, etc.). Following completion of study agent treatment (Visits 2-8), all current medications will be assessed in the follow-up period.
9. Pregnancy test required in Poland only per Inclusion Criteria.

5. Study Treatments

This is a single arm, open-label study. All subjects will receive the investigational treatment ALK4290 at a daily dosage of 800 mg administered orally twice a day as 400 mg tablets for 6 weeks.

6. Sample Size and Power Considerations

A total of 30 subjects will be enrolled in the study with the intent of obtaining approximately 25 evaluable subjects who would complete at least 3 weeks of treatment and evaluations through Visit 5 (Day 22). Subjects who discontinue prior to Day 22 may be replaced. Subjects who withdraw or are withdrawn during screening (prior to completing V2) will be replaced. The study is not powered for detecting statistically significant differences in therapeutic parameters in subjects with wAMD receiving ALK4290.

7. Data Preparation

Data management procedures, including database design and selection of the data dictionary will be performed by the Data Manager and reviewed and approved by the Sponsor. Auto-coding of all AEs, medical histories and concomitant medications will be performed by the IBM Clinical Development EDC system with additional manual coding performed by the Sponsor designated medical coder. Medical coding will be reviewed by the GCT Medical Monitor and confirmed and approved by the Sponsor. All reported study data will be recorded on the electronic Case Report Forms (eCRF) using IBM Clinical Development and transferred to SDC by ProTrials. Clinical personnel at the study site and the CRO are responsible for ensuring that the protocol is followed and that the eCRFs are properly completed.

Additional safety lab data external to the eCRF data will be provided by Synevo to ProTrials to be reconciled with the EDC data and transferred separately to SDC for analysis. External PK data will be transferred from KCAS and will be analyzed by SDC as outlined in the PK plan (separate from the SAP).

[REDACTED]

[REDACTED]

All Subject IDs will be assigned automatically within the EDC. The Subject ID consists of 9 numbers: the first set of 3 numbers are specific for the protocol number (i.e., 201); the second set of 3 numbers are specific for the site number (i.e., 001 through 012), and the third set of 3 numbers are the subject specific screening number (e.g., 001, 002, etc.).

After data are entered into EDC, data are reviewed and verified by the clinical monitoring/operations CRO and ProTrials Data Management. Additionally, SAE reconciliation of the Clinical Database is performed against the Alkahest Global Safety Database and any issues are resolved. When the database has been confirmed to be complete, consistent and accurate, the database will be locked according to ProTrials Standard Operating Procedures and study specific Data Management Plan. Any

changes to the database after that time can only be made with the approval of the Sponsor in consultation with ProTrials and SDC.

Final analyses outlined in this document will be performed after:

- All data management requirements are met according to ProTrials' Standard Operating Procedures (SOP), including performance of edit and verification checks, documentation and resolution of data queries, and database lock with written authorization provided by appropriate ProTrials' and Sponsor personnel;
- All major protocol deviations and the Per Protocol (PP) set have been determined.

8. Analysis Sets

The presentation of baseline characteristics will be based on the Intent-to-Treat (ITT) set. All safety analyses will be performed using the Safety set. Analyses of the primary and exploratory efficacy endpoints will focus on, but will not be limited to, the Evaluable and/or PP sets, as defined below.

8.1 Intent-to-Treat Set

The Intent-to-treat set includes all enrolled subjects.

8.2 Safety Set

The Safety set includes all subjects who received at least 1 dose of the study agent.

8.3 Evaluable Set

The Evaluable set includes all subjects who complete at least 3 weeks of treatment during the 6-week treatment period.

8.4 Per Protocol Set

The Per Protocol set is a subset of the Evaluable set, comprised of all subjects who completed the study and have no major protocol violations.

9. General Statistical Considerations

Final data analysis will be performed by SDC after the study is completed and the database has been cleaned and locked. One interim analysis will be performed by SDC when two-thirds of all enrolled subjects have either completed Day 15 (Visit 4) or prematurely exited the study; at this time, a snapshot of the database will be extracted (without formal pre-database-lock data cleaning) for inclusion in the interim analysis. Statistical programming and analyses will be performed using SAS[®] Version 9.4 or higher.

Unless specified otherwise, all ocular assessments and efficacy outcome measures are with respect to the study eye, hereence. Data collected for the fellow eye (non-study eye) will be included in subject listings and may be analyzed.

Study day will be calculated as (Date of Visit) – (Date of Initiation of Investigational Medicinal Product [IMP]) + 1 for visits after initiation of IMP and as (Date of Visit) – (Date of Treatment Initiation) for visits prior to initiation of IMP.

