5.3.2 HANDLING OF PARTICPANT WITHDRAWALS OR TERMINATION

Approximately 30 subjects will be enrolled in the study. Subjects will be encouraged to complete the study and all assessments. However, subjects may voluntarily withdraw at any time, and the investigator may discontinue individual subjects from the study at any time. For subjects who withdraw consent from the study, no study procedures will be done thereafter. For those that withdraw from receiving the study agent, follow-up visits and the safety phone follow-up are to occur as per the protocol. Excluding cases of medical emergency, but prior to the discontinuation of a subject from the clinical study for disease worsening, the study investigator should discuss each case of discontinuation with the sponsor and/or the medial monitor.

The subject withdrawal criterion below should be used to assess worsening or disease progression. In such cases, a documented assessment by the principle investigator is required, and subjects with clinically significant disease progression should be considered for withdrawal from the study and subsequent initiation of standard of care:

- A BCVA loss of ≥ 5 letters from baseline
- New macular subretinal hemorrhage
- Investigator discretion based on acute worsening of underlying disease or substantial risk to further participation in the study

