10.3 ANALYSIS DATASETS

Four analysis datasets are possible however, analyses may not necessarily be conducted with all four:

- **Intention-to-Treat (ITT) Dataset:** all enrolled subjects
- **Safety Dataset:** all subjects who received at least 1 dose of the study agent
- **Evaluable Dataset:** all subjects who complete at least 3 weeks of treatment during the 6-week treatment period
 - **Per Protocol Dataset:** a subset of the Evaluable Dataset comprised of subjects who have no major protocol violations

The presentation of baseline characteristics will be based on the ITT dataset. All safety analyses will be performed for the Safety Dataset. Analyses of the primary and exploratory endpoints will focus on the Evaluable and/or Per Protocol Datasets.

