13.3 PROTOCOL DEVIATIONS AND VIOLATIONS

A protocol deviation is any noncompliance with the clinical trial protocol or with GCP. The noncompliance may be either on the part of the subject, the investigator, or the study site staff. When deviations occur, corrective actions are to be developed by the site and implemented promptly.

These practices are consistent with ICH E6:

- 4.5 Compliance with Protocol, sections 4.5.1, 4.5.2, and 4.5.3
- 5.1 Quality Assurance and Quality Control, section 5.1.1
- 5.20 Noncompliance, sections 5.20.1, and 5.20.2.

Violations are instances of protocol noncompliance that have the potential to affect the safety of subjects.

Protocol Deviations are instances of protocol noncompliance that DO NOT have the potential to affect the safety of subjects. Protocol Deviations do not require review by the medical monitor.

- *5.20 Noncompliance, sections 5.20.1, and 5.20.2.* **Violations** are instances of protocol noncompliance that DO have the potential to affect the safety of subjects. Violations are a subset of Protocol Deviations.

All instances of protocol noncompliance will be logged and tracked by the site and CRO. Periodic review of Protocol Deviations will inform assessment of site performance.

It is the responsibility of the site to use continuous vigilance to identify and report deviations promptly to the study CRO and/or sponsor. All deviations must be addressed in study source documents. Protocol deviations must be sent to the local IRB/IEC per their guidelines. The site investigator/study staff is responsible for knowing and adhering to their IRB/IEC requirements.

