13.2 Treatment Exposure

Extent of exposure will be calculated in days using the following:

$$\text{Extent of Exposure (days)} = [\text{Date of last dose} - \text{Date of first dose}] + 1$$

Extent of treatment exposure (days) and the total number of doses received for each subject exposed to IMP will be summarized with continuous descriptive statistics using the Safety set. A subject listing of treatment exposure will also be produced.

14. Analysis of the Primary Endpoint

The primary endpoint is the mean change from baseline (Visit 2 / Day 1) to end of treatment (Visit 8 / Day 43) in BCVA letter score of the study eye as measured by the ETDRS testing method using the Evaluable set. BCVA will be measured at the beginning of every study visit and change from baseline for each subject will be calculated as follow-up visit minus baseline visit. Quantitative summary statistics will be used to summarize the BCVA letter score and change from baseline at each visit. A two-tailed, one-sample t-test will be used to assess the mean change from baseline in BVCA letter score at each visit, in which the change from baseline BCVA letter score will be compared to a reference value of zero. The following SAS code will be used to run the one-sample t-test:

```
PROC TTEST H0=0 ALPHA=0.20 DATA=INDATA;
  VAR BCVA_CHG;
RUN;
```

where

- *INDATA* is the name of the input dataset;
- *BCVA_CHG* is the change in BCVA from baseline to the follow-up visit.

A mixed model accounting for repeated measures will also be used to analyze BCVA. This model will include the change from baseline in BCVA letter score as the response variable and baseline BCVA letter score, smoking status and visit as explanatory variables for adjustment. LS means for each visit will be calculated along with corresponding 95% CIs and p-values. SAS code to implement this repeated measures mixed model is as follows:

```
PROC MIXED DATA=INDATA;
  CLASS SUBJID SMOKE VISIT;
  MODEL CHG = BASELINE SMOKE VISIT / DDFM = KR SOLUTION;
  REPEATED VISIT / SUBJECT=SUBJID TYPE=UN;
  LSMEANS VISIT / CL;
RUN;
```

where

- *INDATA* is the name of the input dataset sorted by *SUBJID* and *VISIT*;
- *SUBJID* is the subject ID number;
- *SMOKE* is the subject's smoking history (Never smoked, Ex-smoker, Currently smokes);
- *VISIT* is the visit at which the BCVA letter score was collected;

- *CHG* is the change from baseline in the BCVA letter score;
- *BASELINE* is the baseline BCVA letter score;

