The Kenward-Roger method will be used to determine denominator degrees of freedom. An unstructured variance-covariance matrix will be used for the above repeated measures model. If the model does not converge using the unstructured matrix, the first order autoregressive structure and the compound symmetry structure will be employed, in that order.

The above analyses will be repeated on the PP set as a sensitivity analysis.

Additionally, the number of subjects with change from baseline in BCVA letter score for the following categories will be summarized with counts and percentages:

- ≥ 15 letters;
- ≥ 14 and ≥ 10 letters;
- ≥ 9 and ≥ 5 letters;
- ≥ 4 and ≥ -4 letters;
- ≥ -5 and ≥ -9 letters;
- ≥ -10 and ≥ -14 letters;
- ≤ -15 letters.

BCVA results will also be presented in a data listing. BCVA results in the fellow eye are not included in the analyses but will be included in the listings. BCVA will also be summarized by visit using box plots.

15. Analysis of the Secondary Endpoints

The analyses for secondary endpoints (incidence, seriousness and severity of AEs) will be discussed in the next section as part of the safety analyses. There is no secondary efficacy endpoint for the study.

16. Safety Analyses

Safety will be assessed for the following endpoints using the Safety set:

- Incidence, seriousness, and severity of AEs;
- Observed slit-lamp biomicroscopy values;
- Observed intraocular pressure (IOP) values;
- Changes from baseline in clinical laboratory values;
- Changes from baseline in physical examination;
- Changes from baseline in vital signs.

Adverse events will be presented using frequencies and percentages of subjects.

Other safety endpoints including slit-lamp biomicroscopy, IOP, clinical laboratory values, physical examination, and vital signs will be summarized using descriptive statistics. Changes or shifts from baseline will also be summarized where appropriate. Assessments performed by eye (study eye and fellow eye) will be summarized separately. No statistical inferential testing will be performed for safety variables.

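### The SAP adds study completion to the protocol's Per Protocol definition without declaring it, which drops withdrawn progressors' data and tilts the Per Protocol mixed model and earlier-visit results toward benefit

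*SAP*

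**What the plan says.** - **PP set, protocol.** Protocol 10.3 defines it as "a subset of the Evaluable Dataset comprised of subjects who have no major protocol violations".
- **PP set, SAP.** SAP 8.4 also starts from the Evaluable set but describes PP as "comprised of all subjects who completed the study and have no major protocol violations". SAP 21, which should list changes from the protocol, is marked not applicable. SAP 1 says the SAP's methods supersede the protocol's, so the narrower set governs.
- **Parent set.** SAP 8.3: "The Evaluable set includes all subjects who complete at least 3 weeks of treatment during the 6-week treatment period".
- **Analyses.** SAP 14 defines the primary endpoint as change from baseline to Visit 8 (Day 43) "as measured by the ETDRS testing method using the Evaluable set", tested by a one-sample t-test at each visit. It adds: "A mixed model accounting for repeated measures will also be used to analyze BCVA". Then: "The above analyses will be repeated on the PP set as a sensitivity analysis". No other analysis is given that label.
- **Missing data.** SAP 9.1 imputes partial or missing dates only, so a missing BCVA stays missing.
- **Withdrawal.** Protocol 5.3.2 lists "A BCVA loss of ≥ 5 letters from baseline" among the criteria by which a progressing subject should be considered for withdrawal and standard of care.
- **Completion.** Neither document defines it. Protocol 8.2.3 places end of treatment at Day 43. Protocol 4.1 gives 10 weeks of participation including follow-up, and the schedule in 15.1 puts the trial-completion entry at the Day 71 call.

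**The concern.** A sensitivity analysis is useful when it relaxes an assumption that the primary analysis depends on. In a six-week single-arm study where worsening vision can lead to withdrawal, the fragile assumption is that subjects without a Day 43 value resemble those with one. A PP set restricted to completers does not relax that assumption. It builds it in, by removing the visits that withdrawn progressors did attend.

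At stake is how a reader would interpret agreement between the two sets. If both show a gain, the PP result would look like support, although part of it may come from who was kept. Because the change from the protocol is undeclared, the reader would not be alerted.

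**Working it through.** **1. The plan's own figures.** Protocol 10.5 and SAP 6 give 30 enrolled and about 25 evaluable. The implied loss is 1 − 25/30 = 16.7%. No SD, effect size, power or withdrawal rate is stated, so there is no derivation to reproduce and the size of the bias must rest on assumptions.

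**2. Which subjects the two definitions treat differently.** Assume no other violations, and take completion to mean reaching Day 43.

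| Subject | Evaluable | PP, protocol | PP, SAP |
|---|---|---|---|
| Withdrawn before 3 weeks | out | out | out |
| Withdrawn after 3 weeks, before Visit 8 | in | in | out |
| Stays to Visit 8 | in | in | in |

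Only the middle row differs. Those subjects have BCVA up to withdrawal and none at Day 43.

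**3. Consequence for each analysis.**
- *Day 43 t-test.* It uses observed Day 43 values only. The middle row contributes none, so the result is identical under both definitions.
- *Mixed model.* Under the protocol definition, the early values of the middle row inform the Day 43 mean. With monotone dropout and an unstructured covariance, the visit means follow in sequence: mean(t) = a(t) + Σ b(t,s) × mean(s) over earlier visits s, where a and b are regression coefficients among subjects still observed at t. Under the SAP definition nobody is missing, and (without covariates) the estimate reduces to the completers' observed mean.
- *Earlier-visit means.* The SAP definition removes values that the protocol definition keeps.

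**4. Simulation.** Assumptions not in the documents: SD of the Day 43 change 6, 8 or 10 letters; SD growing with the square root of time; AR(1) correlation 0.8 between visits; probability p of 0.25, 0.5 or 1 of leaving the study at each of Visits 3 to 7 at which the loss is 5 letters or more; no covariates. There were 1,500 trials of 30 subjects per case. Mean change in letters, true mean 0:

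| SD | p | Day 43 t-test, both definitions | Mixed model, protocol PP | Mixed model, SAP PP | Visit 6 mean, protocol PP | Visit 6 mean, SAP PP |
|---|---|---|---|---|---|---|
| 6 | 0.25 | +0.72 | +0.13 | +0.72 | +0.32 | +0.78 |
| 6 | 0.5 | +1.29 | +0.22 | +1.29 | +0.55 | +1.34 |
| 6 | 1 | +1.91 | +0.38 | +1.91 | +0.98 | +1.99 |
| 8 | 0.25 | +1.32 | +0.28 | +1.32 | +0.66 | +1.44 |
| 8 | 0.5 | +2.29 | +0.54 | +2.29 | +1.25 | +2.49 |
| 8 | 1 | +3.41 | +0.86 | +3.41 | +2.03 | +3.61 |
| 10 | 0.25 | +1.83 | +0.40 | +1.83 | +0.97 | +2.03 |
| 10 | 0.5 | +3.33 | +0.90 | +3.33 | +1.86 | +3.57 |
| 10 | 1 | +4.84 | +1.46 | +4.84 | +3.13 | +5.25 |

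In the reference case (SD 8, p 0.5) the narrowing adds 2.29 − 0.54 = 1.75 letters to the mixed model and 2.49 − 1.25 = 1.24 letters at Visit 6. Across the grid the mixed-model difference runs from 0.72 − 0.13 = 0.59 to 4.84 − 1.46 = 3.38 letters. Repeat runs gave +2.25 and +2.27 for the completers' reference value and up to +4.92 at the top of the grid.

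The residual +0.54 under the protocol wording comes from the 3-week Evaluable rule, which both documents share. If every Evaluable subject had been measured at Day 43, the mean would also have been +0.54.

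**5. A declining population.** Protocol 2.2 gives an untreated loss of 10 letters in a year; pro rata over 6 weeks that is 10 × 6/52 = 1.15 letters. With a true mean of −1.15 and the same reference SD and p, the mixed model gives −0.56 under the protocol wording and +1.33 under the SAP wording.

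**6. If completion means Day 71.** A subject who leaves between Visit 8 and Day 71 has a Day 43 value but is removed from the SAP PP set, so the t-test then changes as well. Applying the same p at Visits 8 to 10 (SD constant after Visit 8) moves the PP Day 43 mean in the reference case from about +2.3 to about +4.1, and the range from about +0.7 to +4.9 up to about +1.5 to +7.8.

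**The case against.** The strongest reply is that the primary Day 43 t-test is the same whichever PP wording is used, so the completer bias in that test comes from observed-case analysis and the Evaluable rule. This stands. A reader might infer that the added condition causes the whole bias, or that removing it repairs the t-test. The tables show otherwise, unless completion means Day 71, which is plausible but not stated.

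A reader might also infer that PP excludes all treatment failures. The documents do not say so: withdrawal is only to be considered, after a documented assessment, and Protocol 8.2.3 keeps end-of-treatment and follow-up visits for subjects who stop only the study agent. Those who worsen and stay can remain in PP.

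A further tempting step uses Protocol 13.3, where violations are "instances of protocol noncompliance that have the potential to affect the safety of subjects", to argue that noncompliance affecting only BCVA can never exclude a subject. SAP 7 requires major protocol deviations and the PP set to be determined before final analysis, and 13.3 treats any noncompliance as a deviation. The terms are loose, but that conclusion does not follow.

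Finally, PP is not the primary set, the study is unpowered, and the Evaluable-set mixed model retains pre-withdrawal data. All of this is true. It limits the harm but leaves the definitions in conflict.

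**Conclusion.** The concern holds in a limited form. The two PP definitions conflict, the change is undeclared, and completion is undefined. Where outcome-driven withdrawals occur after week 3, the SAP wording biases the PP mixed model and earlier-visit PP results toward benefit: about 1.75 letters in the reference case, and 0.6 to 3.4 across the assumed grid. For scale, the 80% interval half-width with 25 subjects and SD 8 is 1.318 × 8/√25 = 2.1 letters.

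The direction follows from the documents once such withdrawals happen. The size rests on the assumed SD, correlation and withdrawal probability. The p = 1 rows treat a discretionary criterion as automatic and are an upper bound on that input. The simulation omits the baseline and smoking covariates of SAP 14.

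**What to change.** In SAP 8.4, delete the words *completed the study and*, so that the PP set matches Protocol 10.3. There is then no undeclared change and no need to choose between Day 43 and Day 71 for this set.

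State in SAP 14 that the PP t-test at Day 43 is not evidence of robustness to dropout, since it uses the same observed values as the Evaluable-set test apart from exclusions for violations. Do not add a PP exclusion for prohibited wAMD therapy as part of this change: it could again remove subjects who worsened, stopped the agent and still attended Visit 8.

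The cost is SAP wording only, with no new data or visits. PP results may look less favourable. The change does not remove the observed-case bias in the t-test or the effect of the 3-week Evaluable rule.
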